Sponsor	NHS R&D National Coordinating Centre for Health Technology Wessex Institute for Health Research & development [name]
	[contact] [contact]
Date	26/11/2007 Version 6

Information contained in this document is the property of Leicester University and is therefore provided to you in confidence for review by you, your staff, or an applicable ethics committee. This information may not be disclosed to others without written approval from the Principal Investigator, except to the extent necessary to obtain informed consent from those persons entering the study. This document may not be reproduced, stored in a retrieval system or transmitted in any form or by any means without prior authorisation from the Principal Investigator. This document must be returned to the Principal Investigator upon request.

	PROTOCOL SYNOPSIS
Title	Randomised controlled trial to evaluate impact of diagnostic testing for influenza, respiratory syncytial virus and Streptococcus pneumoniae infection on the management of acute admissions in the elderly and high risk 18-64-year-olds.
Sponsor	NHS R&D National Coordinating Centre for Health Technology Assessment
Study population	Male or female elderly ( $\geq$ 65 years old) patients, Male or female patients aged $\geq$ 18 years with underlying heart or lung disease including asthma , or pneumonia / influenza type symptoms.
Study setting	Medical Admissions Units in the University Hospitals of Leicester NHS Trust (Leicester Royal Infirmary, Glenfield Hospital, Leicester General Hospital).
Duration	August 1 2005- July 31 2008 (36m). Patient enrolment will occur during September 1 2005 to June 30 2006; September 1 2006 to June 30 2007; & September 1 2007 to June 30 2008 All patients will be followed-up for 28 days.
Rationale	The purpose of this study is to determine the diagnostic accuracy and clinical- and cost-effectiveness of rapid molecular and near patient diagnostic tests for influenza, RSV and S. pneumoniae infections in the elderly, and subjects aged $\geq 18$ years with chronic cardiopulmonary conditions, or pneumonia / influenza type symptoms. in comparison to traditional laboratory culture.

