#### 1.10 The EuroQol Instrument

The EuroQol instrument assesses quality of life by means of 5 questions with three possible answers to each question and produces valuations on a scale which has fixed points of 1 (full health) and 0 (death). It has been widely used in economic evaluations of health care interventions. The EuroQol can be used to generate the outcome of 'Quality Adjusted Life Years' (QALYs) where quality of life in any health state is combined by the duration of that health state. Three different versions of the EuroQol instrument are available. These are a patient self-complete form, a form for completion by interview, and a proxy form (Appendix I).

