#### **1.11** Rationale for the study

Rapid near patient testing for influenza and pneumococcal infection, and rapid molecular tests for influenza and RSV will be justified if, as expected from existing knowledge, it can be shown that:

- Influenza, RSV, & *S. pneumoniae* infections occur as frequently as expected in the target population in the UK, & have an important impact on morbidity, mortality and quality of life.
- Rapid near patient and molecular tests are as reliably sensitive and specific in elderly patients admitted to a UK hospital as they are in other populations and settings; they are as easy to use as expected; and they provide clinically useful data to clinicians as rapidly as expected.
- Rapid diagnostic tests improve the opportunities for infection control in hospitals as expected by reliably identifying patients who, unless isolated, may transmit influenza or RSV to vulnerable patients and staff.
- Rapid diagnostic tests prevent or minimise unnecessary use of antibiotics in patients with viral infections.
- Rapid diagnostic tests aid therapeutic decisions in patients with CAP.
- Rapid diagnostic tests are not associated with increased morbidity or mortality in patients whose treatment would have been different without knowledge of the pathogen.

The selected study population is a key component of the recurrent bed crises experienced by the NHS in winter. Ironically, specific infective diagnoses are rarely obtained in these patients. This reflects the widespread perception that conventional test results are of dubious value, are usually available too late and that empirical therapy offers the best approach to management. As a result, very few centres have a clear view of the major pathogens responsible or have policies that take such information into account. Nonetheless, such information could and should have a profound influence on 1) antibiotic and antiviral use,

2) patient isolation and nursing policies, and 3) policies for immunisation of staff and the local community. Moreover, the timely provision of results through technologies to be assessed could transform attitudes to the value and applicability of results. Thus, while technology assessment is the primary driver and will be decisively achieved by our design, we contend that our proposal embodies exceptional added value by providing essential epidemiological data relating to a major burden on the NHS.

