The costs of performing rapid molecular and near patient diagnostic tests for influenza, RSV and S. pneumoniae infections, differ significantly from the cost of traditional laboratory culture.

6. Assess cost-savings associated with earlier use of narrow-spectrum antimicrobial therapy (or avoidance or discontinuation of antibiotics) in patients whose influenza, RSV and *S. pneumoniae* infections are diagnosed more rapidly by rapid molecular and near patient diagnostic tests, in comparison to traditional laboratory culture.

The earlier use of narrow-spectrum antimicrobial therapy (or avoidance or discontinuation of antibiotics) in patients whose influenza, RSV and S. pneumoniae infections are diagnosed more rapidly by rapid molecular and near patient diagnostic tests results in significant cost-savings, in comparison to traditional laboratory culture.

7. Compare the outcome of patients whose influenza, RSV, and *S. pneumoniae* is diagnosed more rapidly by rapid molecular and near patient diagnostic tests, compared to those who are diagnosed by traditional laboratory culture.

A streamlining of antimicrobial prescribing that may arise from more rapid diagnosis of influenza, RSV and S. pneumoniae infections by rapid molecular and near patient diagnostic tests does not adversely affect patient outcome.

8. Assess the impact that rapid molecular and near patient diagnostic tests have on the costs associated with an inpatient stay and on costs post-discharge up to a maximum of 28 days after admission.

Any increase in costs incurred by rapid molecular and near patient diagnostic tests, in comparison to traditional laboratory culture, is more than offset by savings that arise from either rational antimicrobial prescribing or earlier discharge from the hospital.

9. To assess the impact that rapid molecular and near patient diagnostic tests have on quality-of-life, as measured by the EuroQol (Appendix I), and to use this information to estimate the quality adjusted life years (QALYs) generated during the 28 days after admission.

Rapid molecular and near patient diagnostic tests result in an improvement in quality-of-life, as measured by the EuroQol, which arises from streamlining of antibiotics and earlier discharge into the community.

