10. To assess the cost-effectiveness of rapid molecular and near patient diagnostic tests in comparison to the cost/QALY of cases diagnosed correctly by traditional laboratory culture. To assess the costeffectiveness of rapid molecular and near patient diagnostic tests in comparison to traditional laboratory culture. This will be done on the basis of both cost per case detected and cost per QALY.

Rapid molecular and near patient diagnostic tests are more cost-effective than traditional laboratory culture.

11. To explore whether patients with pneumococcal infection have lower levels of cellular and humoral immunity to the pneumococcus in comparison to patients who do not have pneumococcal infection.

Patients with pneumococcal infection have lower levels of cellular and humoral immunity to the Pneumococcus in comparison to patients who do not have pneumococcal infection.

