the different microbiological tests for influenza, RSV, and *S. pneumoniae*, together with the results, will be documented

*Treatment* The nature (name, dose, frequency, and route of administration) of all antimicrobials given to all patients within 10 days of admission will be documented. Note will be made of when 'broad-spectrum' treatment is switched to 'narrow-spectrum treatment'; when intravenous antibiotics are switched to oral therapy; and when antibiotics are discontinued. The requirement for supplemental oxygen will also be documented.

*Isolation status, admission to ITU, and ventilatory support* A record will be kept of (i) the patient's isolation status during the first 7 days of admission, and whether the patient was admitted to an ITU and/or required ventilatory support (including ward-based CPAP) during the first 10 days of admission.

*Pyrexia* The time (24 hr clock and date) during the patient's first 10 days of hospitalisation (or until death, if relevant) when the patient first became apyrexial (temperature  $\leq 37.2^{\circ}$ C), and remained so for a period of >24 hours will be recorded.

*Convalescent serology* A convalescent blood sample will be collected for paired acute and convalescent serology for influenza and RSV at 10 -90days.

*Diagnostic studies* The nature and results of all diagnostic studies (e.g., chest radiograph, ECG, full blood count, cardiac enzymes, PaO2) carried out by the medical team will be recorded.

*EuroQol* The health status of all patients will be assessed by the EuroQol on days 7 and 28. Where patients have been discharged the EuroQol will be assessed by telephone interview of the patient or by postal questionnaire or by proxy (Appendix I).

*Humoral and cell-mediated immunity to the pneumococcus.* Patients whose antigen tests for the pneumococcus are positive and an equivalent number of people whose pneumococcal test is negative will be bled on one occasion only within 5 days of hospital admission, for tests of cellular and humoral immunity to the pneumococcus.

Physical Activity Questionnaire will be completed on day 2 or 3.

*Deaths* Deaths that occur within a maximum 28 days of hospitalisation will be identified by the study nurse and recorded in the CRF. [Note: the principal investigator MUST be notified by the study nurse of all deaths that occur within 28 days of admission and of the patient's study group].

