#### 6.2.9 Quality of Life assessment (Days 7 and 28)

All patients will be assessed by the EuroQol (Appendix I) on Days 7 and 28, and the results recorded in the CRF. Patients who have been discharged will be assessed by post using a questionnaire, or by a simple telephone interview.

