  First, the proportion of patients with *S. pneumoniae* infection in Groups 1, 2, and 3.
  Second, to better define the burden of influenza and RSV, the proportion of all patients with (i) influenza, and (ii) RSV, who die.
- 3. Quality of life, as measured by EuroQol, and quality adjusted life years generated during the 28 days after admission, will be assessed:
  - (a) In all patients in Groups 1, and 2 in comparison to Group 3.

- (b) Second, in patients in patients with (i) influenza, (ii) RSV, and (iii) *S. pneumoniae* in Groups 1, and 2, in comparison to Group 3.
- 4. Use of isolation facilities
  - (a) The time from admission to the MAU to the time of admission to a single room (isolation cubicle) will be compared for patients with confirmed influenza or RSV in Groups 1, 2, and 3.
  - (b) The proportion of patients with influenza or RSV in Groups 1, 2, and 3 who are isolated at any stage during the first 120 hours of the admission.
  - (c) The proportion of patients with *S. pneumoniae* infection in Groups 1, 2, and 3 who are inappropriately isolated for >12 hours.

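### QALYs stop at Day 28, so cost per QALY leaves out life-years lost to any mortality difference and the QALY difference can carry the wrong sign

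*Protocol*

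**What the plan says.** Section 2.1, objective 9, sets out to "estimate the quality adjusted life years (QALYs) generated during the 28 days after admission". The endpoint in section 7.5.1, item 3, repeats the window: "quality adjusted life years generated during the 28 days after admission, will be assessed". Objective 10 then covers cost-effectiveness: "This will be done on the basis of both cost per case detected and cost per QALY". Section 7.5.2, item 4, lists the same two measures as the main economic outcomes. Neither objective 10 nor that endpoint restates 28 days, but no other QALY is defined anywhere in the protocol.

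The window matches data collection. The synopsis says "All patients will be followed-up for 28 days"; section 6.2.9 says "All patients will be assessed by the EuroQol (Appendix I) on Days 7 and 28", in addition to a baseline assessment; and section 4.1 says "Deaths that occur within a maximum 28 days of hospitalisation will be identified by the study nurse and recorded in the CRF". Section 1.10 anchors the EuroQol scale at 1 for full health and 0 for death.

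On costs, objective 8 also stops at 28 days. However, the Cost Data paragraph of section 7.6 provides for estimating costs over longer periods by extrapolation from discharge times. It states nothing equivalent for survival or QALYs.

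**The concern.** The protocol itself treats excess mortality as a possible harm of rapid testing. Sections 1.5, 3.5 and 10.4 describe how it could arise: early narrowing of antibiotics in a patient whose infection is polymicrobial. Section 1.11 makes it a condition of adopting the tests that "Rapid diagnostic tests are not associated with increased morbidity or mortality" in patients whose treatment would otherwise have been different. The savings hypothesised under objective 8 come from changed prescribing and earlier discharge, so the feared harm and the hoped-for saving share a mechanism.

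A QALY that stops at Day 28 values a death only by the part of those 28 days that is lost. Years lost afterwards count as zero. A policy that causes deaths is undercharged and one that prevents them is under-credited, in the ratio meant to answer objective 10.

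Two features of the costing add to the imbalance:
- Costs may run past Day 28 while QALYs cannot. The protocol does not say which cost horizon enters the ratio.
- Inpatient cost is built from length of stay (synopsis, Care costs), and stay is recorded to discharge or death (section 6.2.10). An early in-hospital death can therefore lower recorded cost.

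**Working it through.** The protocol states no QALY figure, so there is none to reproduce. The cap follows from its own inputs; everything beyond the cap needs assumptions, which are marked.

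**1. Cap per death (protocol inputs only).** Horizon 28 days; utility between 1 and 0.
- Maximum loss = 28/365 × (1 − 0) = 0.077 QALY. This is death at admission against otherwise full health.
- Largest effect on the mean per patient: 1 point of mortality, 0.01 × 0.077 = 0.0008; 2 points, 0.0015; 5 points, 0.0038.
- A utility difference of 0.02 held for 28 days is also worth 0.02 × 0.077 = 0.0015. So 2 points of mortality weigh at most as much as 0.02 of utility.
- A more typical loss, with death at day 14 and utility 0.6 (assumed): 14/365 × 0.6 = 0.023 per death, or 0.0005 per patient for 2 points.

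**2. What a death is worth beyond Day 28 (assumed 1 to 10 years at utility 0.4 to 0.8, undiscounted).**
- Low: 1 × 0.4 = 0.4 QALY; 0.4/0.0767 = 5 times the cap.
- Middle: 5 × 0.6 = 3.0 QALYs; 39 times the cap.
- High: 10 × 0.8 = 8 QALYs; 104 times the cap.

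**3. Can the sign change? (illustration).** Assume the rapid arm gains 0.03 utility throughout the 28 days, has 2 points excess mortality, and its extra deaths fall on day 14. The quality-of-life gain is 0.03 × 0.0767 = 0.0023 QALY. The loss inside the window is 0.02 × 14/365 × utility; the loss after it is 0.02 × the value from step 2.

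| Assumed later survival | QALY difference at Day 28 | With later life-years counted |
|---|---|---|
| 1 year at 0.4 | 0.0023 − 0.0003 = +0.0020 | +0.0020 − 0.008 = −0.006 |
| 5 years at 0.6 | 0.0023 − 0.0005 = +0.0018 | +0.0018 − 0.06 = −0.058 |
| 10 years at 0.8 | 0.0023 − 0.0006 = +0.0017 | +0.0017 − 0.16 = −0.158 |

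In this illustration the sign reverses across the whole assumed range.

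**4. What happens to the ratio itself.** With an assumed cost difference of 50 units and the middle row, cost per QALY without excess mortality is 50/0.0023, about 21,700. With 2 points excess mortality it is 50/0.00184, about 27,200, which is 25% higher. The 28-day ratio does respond to mortality, but it still shows a QALY gain where the longer horizon shows a loss.

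**5. How precise a longer-horizon analysis would be.** Take 2752 patients less the planned 20% dropout, over three groups: about 734 per arm. Section 1.5 gives about 2.5% mortality for pneumococcal pneumonia; applying it to all patients is an assumption.
- 95% half-width for a mortality difference: 1.96 × √(2 × 0.025 × 0.975/734) = 0.016, or 1.6 points.
- In QALYs per patient: 0.016 × 0.4 = 0.006; × 3.0 = 0.048; × 8 = 0.13.

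These half-widths are of the same order as the losses in step 3.

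**The case against.** The best defence is that mortality is handled elsewhere. Section 7.6 compares it by log-rank test, Kaplan-Meier curves and Cox regression; objective 7 addresses harm from streamlining; section 1.5 plans interim analyses by an independent committee; and section 1.11 makes absence of increased mortality a condition in its own right. A reader might infer that cost per QALY is the trial's only protection against adopting a harmful policy. It is not. Nor does section 10.4 rule the tests out if deaths rise: it sets reporting duties to the monitoring committee. What survives is narrower: none of these provisions corrects the ratio used for objective 10. The mortality comparison is also a weak substitute. Power was estimated only for accuracy, length of stay and isolation, and with about 73 elderly pneumococcal cases per group at 2.5% mortality, one expects about 2 deaths per group.

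Second, a 28-day horizon is coherent with follow-up and with objective 8, and a modelled extension is often left to a later economic plan. Only the protocol was available, so such an analysis may exist elsewhere. But the protocol is not silent: it fixes the QALY window and provides for extrapolating costs alone.

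Third, a reader might infer that a mortality difference hardly moves the economic result. Step 4 shows otherwise: quality-of-life gains are capped by the same window, so the ratio can shift noticeably. It would also be too strong to say savings count in full, because objective 8 limits costs to 28 days and section 7.6 only opens the possibility of a longer horizon.

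Fourth, an extended analysis would be noisy, since chance deaths could dominate it (step 5). That stands. It argues for showing the uncertainty and against any rule that both horizons must agree before a conclusion is drawn.

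**Conclusion.** The concern holds in a limited form. The QALY is fixed at 28 days, a death can cost no more than 0.077 QALY, and life-years lost later are dropped from a main economic outcome whose cost side may run longer. If mortality differs between arms, the sign of the QALY difference can be wrong.

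The cap is firm. The size of what is omitted is not: 5 to 104 times the cap rests on assumed survival and utility, for which the protocol gives no figures. A single large multiplier would claim more than the documents support. The reversal shown is an illustration under assumed effects, not a prediction that mortality will differ. The 28-day analysis is valid as a within-trial result; the weakness is relying on it alone to call the tests more cost-effective. This should be corrected, but it does not invalidate the design.

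**What to change.** Keep the 28-day cost per QALY. Label it within-trial in objective 10 and section 7.5.2, and state that its costs use the same 28-day horizon.

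Add a required secondary analysis that:
- charges each death by Day 28 with age- and sex-specific remaining life expectancy, discounted;
- varies that expectancy over a stated range, for example 25% to 100% of the life-table value, because these patients are sicker than the general population;
- varies the utility applied to the remaining years, since a Day 28 EuroQol taken in early convalescence may not represent them;
- carries the sampling uncertainty of the mortality difference into the QALY and cost-per-QALY intervals.

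Report both analyses. If they differ, say that the cost-effectiveness conclusion depends on the horizon. Agreement between them need not be a condition for drawing a conclusion.

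The cost is a short additional analysis. Age, sex, deaths to Day 28 and EuroQol at Day 28 are already collected, so no new visit or patient is needed. The drawback is reliance on an outside survival assumption and wide intervals, because deaths are few.

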#### 2.2 Observational objectives and hypotheses

In the Medical Admissions Units/Wards of the University Hospitals of Leicester, to:

11. Estimate the admission rates for influenza, RSV, and S pneumoniae in the target population.

The admission rates in the target population are higher for S pneumoniae than influenza A and B. The admission rates for influenza A and B are similar to those for RSV A and B.

12. Compare the clinical characteristics and economic burden of influenza A and B and RSV A and B.

The clinical characteristics and economic burden of influenza A and B and RSV A and B are similar.

13. Review the implications of rapid diagnosis on isolation policy, and review alternate approaches to managing the infection control issues.

Rapid near patient and/or molecular diagnostic tests will reveal more cases of influenza and RSV who require isolation than can be isolated. Alternate approaches to managing the infection control issues, such as the use of influenza neuraminidase inhibitors, may be pertinent.

## 3 STUDY APPROVAL, CONSENT, ASSENT, AND PATIENT CONFIDENTIALITY

#### 3.1 Declaration of Helsinki

This study will be conducted according to the 'Declaration of Helsinki' (as amended in Tokyo, Venice, Hong Kong, South Africa, 1996 and the 52nd WMA General Assembly, Edinburgh, Scotland, October 2000) (For Declaration of Helsinki, see Appendix II).

#### **3.2** Ethics committee approval

This protocol and any accompanying material provided to the patient (such as patient information sheets or descriptions of the study used to obtain informed consent), will be submitted by the principal investigator to the Leicester Ethics Committee and to any other relevant Ethics Committee. Approval from the Committee must be obtained before starting the study, and should be documented in a letter to the investigator specifying the date on which the committee met and granted approval for the study and the protocol identification (title, version, date).

Any modifications made to the protocol after receipt of the Ethics Committee approval must be submitted by the investigator to the Committee in accordance with local procedures.

#### 3.3 Patient informed consent/assent from a relative or carer

*Patients who are capable of providing consent* It is the responsibility of the clinical investigators or their deputies (Research Nurses/non-Consultant medical staff taking part in the study) to obtain signed informed consent from all prospective trial participants who are considered capable of providing consent (by the nursing and/or medical team providing clinical care). For such people signed informed consent will be obtained prior to entry to the study, after adequate explanation of the aims, methods, objectives, and potential hazards of the study, including any discomfort it may entail. Subjects will be given every opportunity to clarify any points they do not understand and if necessary ask for additional information. Prospective trial participants will be given time to reflect on their participation for a period not exceeding 8 hours of initial assessment by the admitting doctor on the Medical Admissions Unit, or another ward accepting acute medical admissions.

The clinical investigators or their deputies (Research Nurses/non-Consultant medical staff taking part in the study) must also explain to patients that they are completely free to refuse to enter the study or to withdraw from it at any time for any reason, without incurring any penalty or loss of any benefit to which they are otherwise entitled. Appropriate forms for documenting written informed consent will be provided by the Principal Investigator. Signed informed consent forms must be kept on file by the investigators in the Study Coordinating Centre (Infectious Diseases Laboratory, Leicester Royal Infirmary) and the collection of informed consent must be documented in the case report form. The clinical investigator, or his/her designee (Research Nurses/Research Doctor taking part in the study) must document in the case report form that informed consent was obtained BEFORE any trial specific procedures are performed on the subject.

*Patients who are incapable of providing consent* The Study Nurses or medical staff taking part in the study may additionally approach an accompanying relative, or a carer, of patients who can not give signed informed consent either because: (a) they are so breathless or confused that they are temporally unable to assimilate information regarding the study to judge whether to participate; or (b) the patient has pre-senile or senile dementia. In such cases, the study nurse or study doctor will seek informed Assent from either the patient's relative or a carer. The clinical investigators or their deputies must also explain to relatives or carer that they are completely free to refuse assent to enter the study or to withdraw it at any time for any reason, without incurring any penalty or loss of any benefit to which the patient is otherwise entitled. Appropriate forms for

documenting signed informed assent will be provided by the Principal Investigator. The clinical investigator, or his/her designee must document in the case report form that assent was obtained BEFORE any trial specific procedures are performed on the subject. The study nurse or study doctor will subsequently approach patients whose recovery enables them to provide signed informed consent.

